## 2. LIST OF ABBREVIATIONS

Abbreviation	Definition
AE	adverse event
AEM	adverse event monitoring
BMI	body mass index
CI	confidence interval
CR	complete response
CRP	C-reactive protein
CSA	clinical study agreement
DCF	data clarification form
DCT	data collection tool
ECOG PS	Eastern Cooperative Oncology Group Performance Status
eCRF	electronic case report form
EDC	electronic data capture
eGFR	estimated glomerular filtration rate
ENCePP	European Network of Centres for Pharmacoepidemiology and Pharmacovigilance
IEC	Independent Ethics Committee
IMDC	International Metastatic RCC Database Consortium
irAE	Immune-related adverse event
IRB	Institutional Review Board
mRCC	metastatic renal cell carcinoma
NIS	non-interventional study
OR	objective response
PD-L1	programmed death ligand 1
PFS	progression-free survival
PD	progressive disease
PR	partial response
RCC	renal cell carcinoma
SAP	Statistical Analysis Plan
SD	stable disease
SD	standard deviation
TKI	tyrosine kinase inhibitor
TNM	tumor-node-metastasis
TTF	time to treatment failure

YRR	your reporting responsibilities
-----	---------------------------------

PFIZER CONFIDENTIAL

### 3. RESPONSIBLE PARTIES

#### Principal Investigator(s) of the Protocol

List of Principal Investigators in this study will be prepared as *Annex 1*.

### 4. ABSTRACT

Not applicable

### 5. AMENDMENTS AND UPDATES

Amendment number	Date	Protocol section(s) changed	Summary of amendment(s)	Reason
2.0	25 Oct 2021	2. LIST OF ABBREVIATIONS, 6. MILESTONES, 9.3. Variables, 10.2.1. For subjects who are alive and still visit the study site, 10.2.2. Subjects who are alive and had been transferred to another medical facility, 10.2.3. Subjects who are deceased, 10.2.4. Handling of study results, etc, 10.2.4.1. Response to important findings and other information concerning the health of subjects, 10.4. Institutional review board (IRB)/Independent ethics committee (IEC), 10.5. Ethical conduct of the study, 10.8. Registration and publication of study, 10.9. Secondary use of specimens and information obtained from subjects, ANNEX 1. LIST OF STAND ALONE DOCUMENTS	2. Deleted the description regarding UMIN-CTR, 6. changed the planned date of milestone, 9.1.2. delete "and/or", 9.3. added the description that this study will not collect human genome and gene information, 10.2.1. added "Handling of results and other information obtained from the study", 10.2.2. amended the name of the ethics guidelines, 10.2.3. amended the name of the ethics guidelines, 10.2.4. added policy for the explanations of study results, etc., 10.2.4.1. added the description regarding response to important findings and other information concerning the health of subjects, 10.4. added the method of review handling, 10.5. amended the name of the ethics guidelines, 10.8. delete the description regarding UMIN-CTR, 10.9. added the details of methods of the handling secondary use, ANNEX 1. added "The responsible parties of the study"	2. to correct typos, 6. to amend the schedule, 9.1.2. to correct typos, 9.3. to clarify that this study will not collect human genome and gene information, 10.2.1. because ethic guidelines has been revised, 10.2.2. because ethic guidelines has been revised, 10.2.3. because ethic guidelines has been revised, 10.2.4. because ethic guidelines has been revised, 10.2.4.1. because ethic guidelines has been revised, 10.4. because ethic guidelines has been revised, 10.5. because ethic guidelines has been revised, 10.8. to correct typos, 10.9. to add the details, ANNEX 1. to correct typos

## 6. MILESTONES

Milestone	Planned date
Observation period	from index date to 20 Jun 2021
Start of data collection	08 Sep 2021
End of data collection	31 Jan 2022
Analytical dataset lock	31 Jan 2022
Final study report	31 May 2022

## 7. RATIONALE AND BACKGROUND

Approximately 30,000 patients were diagnosed with renal cancer in Japan in 2017 , and the number of cases has been increasing annually since the 1980s.

Recently, the immunotherapeutic approaches have demonstrated clinical efficacy in several cancer types, and some immune checkpoint inhibitors have been approved for the treatment of renal cell carcinoma (RCC). One of them is avelumab, which is an anti-programmed death ligand 1 (PD-L1) antibody. In December 2019, avelumab plus axitinib combination therapy was approved as a first-line treatment for the unresectable or metastatic renal cell carcinoma (mRCC) in Japan. This is the first-line therapy approved in Japan that combines an immuno-oncology drug with a tyrosine kinase inhibitor (TKI) to treat the patients with RCC.

Several clinical studies have been focused on this therapy for the treatment of RCC, but no real-world data have been collected in Japan. Therefore, the patient's background, treatment status, and outcomes of avelumab plus axitinib combination therapy must be clarified in the real-world clinical settings in Japan.

The Phase 3 JAVELIN Renal 101 trial was conducted to compare avelumab plus axitinib combination therapy with sunitinib monotherapy in previously untreated patients with advanced RCC. The results showed that the progression-free survival (PFS) was significantly longer in patients who were treated with avelumab plus axitinib (median: 13.8 months; 95% confidence interval [CI]: 11.1 to inestimable months) than in those treated with sunitinib (median: 7.2 months; 95% CI: 5.7–9.7 months; hazard ratio for disease progression or death: 0.61; 95% CI, 0.47–0.79;  $P <0.001$ ) . Therefore, more than a 1-year of follow-up period is required to assess the real-world effectiveness of this combination therapy, such as PFS. Three studies with long-term follow-up periods were planned. In the present study, B9991043 is to evaluate the current treatment outcomes after a 1-year launch in patients with mRCC treated with avelumab plus axitinib as a first-line therapy. In the future, two other

observational studies will be conducted with follow-up periods of two and five years as per the plan.

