#### **9.1.3.2. Real-world PFS**

Real-world PFS is defined as the following:

- Real-world PFS, defined as time from start of avelumab/axitinib treatment to date of first disease progression (as clinically assessed by local investigator based on radiology, laboratory evidence, pathology, or other assessments) or death due to any cause, whichever came first  
If there were no clinical records of death or disease progression, they were censored at the date of initiation of the next line of therapy for the patients undertaking two or more lines of therapy based on the record, or at their last visit date during the study period for the patients undertaking only one line of therapy based on the record.

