### **9.3.3. Clinical outcome (Real-world PFS)**

Definitions of Real-world PFS is defined in [Section 9.1.3](#). The following data will be collected to determine the clinical outcomes: date of start of treatment, date of first disease progression or death due to any cause, whichever came first.

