### **10.3.2. Subjects who are deceased**

When the subjects' legally acceptable representatives refuse to participate in the study during the study period, all of their data must be excluded from the analysis dataset. If the results of this study are disclosed on paper or conference at the time of refusal, the subject's data cannot be excluded.

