6.3 Derivation variables

1) Survival time analysis

It is defined as follows:

Endpoint	Start date	End date (event)	End date (censor)
Real-world PFS	Date treatment with avelumab and/or axitinib was initiated (if not on the same day, whichever occurs earlier)	Date of first disease progression (clinical evaluation based on radiological, laboratory, pathological, or other evaluation by the principal investigator) or death from any cause, whichever occurs earlier	Date of last confirmation of progression-free survival or start of subsequent treatment (whichever occurs earlier)
TTF of avelumab and axitinib	Date treatment with avelumab and/or axitinib was initiated	Date of completion of treatment with avelumab and/or axitinib	Date of last confirmation of progression-free survival or date of last dose in case of efficacy stopping (whichever date occurs earlier)
TTF of avelumab	Date treatment with avelumab was initiated	Date of completion of treatment with avelumab	Date of last confirmation of progression-free survival or date of last dose in case of efficacy stopping (whichever date occurs earlier)
TTF of axitinib	Date treatment with axitinib was initiated	Date of completion of treatment with axitinib	Date of last confirmation of progression-free survival or date of last dose in case of efficacy stopping (whichever date occurs earlier)

2) Objective response rate

ORR is defined as the proportion of patients with a CR or PR as the best overall response in tumor assessment during the observation period, as assessed by an investigator under actual clinical practice, including assessment based on RECIST ver. 1.1.

3) Calculation of duration

Duration	Definition
Duration of avelumab treatment	Date of last dose – date of initial dose + 14
Duration of axitinib treatment	Date of last dose – date of initial dose + 1
Duration of non-administration	Date of end – Date of start + 1

4) Corticosteroid equivalent dose (prednisolone equivalent)

This will be calculated as shown in the table below.

Generic name	Corresponding amount (mg)	Prednisolone conversion ratio
Cortisone	25	0.2
Hydrocortisone	20	0.25
Prednisolone	5	1
Methylprednisolone	4	1.25
Triamcinolone	4	1.25
Dexamethasone	0.75	6.7
Betamethasone	0.6	8.3

5) Date of initial dose

If avelumab and axitinib are administered for different durations, the earlier of the two dates should be used as the date of the initial dose.

6) Date of last confirmation of progression-free survival

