8.3.3.3 Duration of corticosteroids treatment for irAE during avelumab plus axitinib treatment

Analysis set	Analysis population
Details of analysis	Perform the same analysis as in 8.3.3.2 for duration of corticosteroid treatment.
Supplement	If the patient is on continuous corticosteroid treatment, the period should be up to the cut-off date (20 June, 2021).

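### Does leaving 20 June 2021 out of the PFS and TTF rules bias those endpoints, or undercut the follow-up that Section 7 calls for?

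*Protocol*

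**What the plan says.** Protocol Section 7 cites a median PFS of 13.8 months from the pivotal trial and concludes that "more than a 1-year of follow-up period is required to assess the real-world effectiveness of this combination therapy, such as PFS". It then presents this study as the first of three, looking at outcomes about a year after launch, with two- and five-year studies to follow.

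Protocol Sections 6 and 9.1 and SAP Section 4 give one observation period for the whole study, from the index date to 20 June 2021. They make no exception for any endpoint. Charts are abstracted from 8 September 2021 to 31 January 2022 (Protocol Section 6).

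The endpoint rules are worded unevenly:

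- **Protocol 9.1.3.2** sets no date limit on progression or death. It censors first-line-only patients "at their last visit date during the study period for the patients undertaking only one line of therapy based on the record", and does not define that period.
- **Protocol 9.3.3** asks sites for the "date of first disease progression or death due to any cause, whichever came first", with no end date.
- **SAP 6.3, PFS censoring:** "Date of last confirmation of progression-free survival or start of subsequent treatment (whichever occurs earlier").
- **SAP 6.3, all three TTFs:** "Date of last confirmation of progression-free survival or date of last dose in case of efficacy stopping (whichever date occurs earlier").
- **SAP 6.3, response rate:** limited to the "best overall response in tumor assessment during the observation period".
- **SAP 8.3.3.3, ongoing corticosteroids:** "the period should be up to the cut-off date (20 June, 2021").

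SAP Section 9 declares no changes from the protocol.

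**The concern.** Two things look wrong.

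First, a plan that asks for more than a year of follow-up gives its last entrants six months.

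Second, the SAP states the end date for response and corticosteroid duration but not for PFS or TTF. A programmer could take the silence as deliberate. Because charts are read well after 20 June 2021, later progressions, deaths and treatment ends can be on record. If those were counted while event-free patients were censored at the cut-off, the analysis would keep late failures and drop the event-free time that belongs with them. PFS would come out too short and its confidence interval would cover too rarely. PFS and TTF carry the efficacy objective, and the results are meant for publication.

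**Working it through.** The documents give no event count or follow-up in months, so there is no planned figure to reproduce.

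**Inputs.** Entry 20 December 2019 to 20 December 2020 (Protocol 9.1); end of observation and abstraction dates (Protocol Section 6); 30.4375 days per month (SAP 6.2); about 70 patients (Protocol 9.5); benchmark median 13.8 months (Protocol Section 7). Assumed: even entry, exponential PFS, no other censoring.

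**Follow-up and expected events.** With λ = ln 2 / 13.8 = 0.0502 per month and potential follow-up spread evenly from a to b months,

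P(event) = 1 − [exp(−λa) − exp(−λb)] / [λ(b − a)].

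For the cut-off, a = 182/30.4375 = 5.98 and b = 548/30.4375 = 18.00. This gives 1 − (0.7406 − 0.4048)/0.604 = 0.444, and 70 × 0.444 = 31.1 events.

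| Follow-up to | Days | Months | More than 1 year | Events of 70 |
|---|---|---|---|---|
| 20 June 2021 | 182-548 | 6.0-18.0 | 49.9% | 31.1 |
| 8 September 2021 | 262-628 | 8.6-20.6 | 71.7% | 35.9 |
| 31 January 2022 | 407-773 | 13.4-25.4 | 100% | 43.2 |

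So 35.9 − 31.1 = 4.8 to 43.2 − 31.1 = 12.1 first events could fall between the cut-off and chart reading.

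**Effect on the estimate.** Kaplan-Meier on 400,000 simulated patients, true median 13.8, true 12-month PFS exp(−0.0502 × 12) = 0.547. Ranges run from all charts read on 8 September 2021 to all read on 31 January 2022.

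| Rule applied | Median | 12-month PFS |
|---|---|---|
| Cut-off on events and censoring | 13.8 | 0.547 |
| Cut-off on neither | 13.8 | 0.547 |
| Later events counted, event-free patients censored at cut-off | 12.1-12.3 | 0.505-0.510 |
| Events stopped at cut-off, event-free time credited beyond it | not reached | 0.58-0.59 |

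In simulated studies of 70, coverage of the interval for the median is about 95% in the first row. In the third it is 87% (all charts read on 8 September) or 81-82% (readings spread to 31 January).

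**Which rows the text supports.** Sections 6 and 9.1 and SAP Section 4 give the first row. SAP 6.3 taken alone leaves both its event and its censoring columns undated, which is the second. The third row needs the undefined period in Protocol 9.1.3.2 to be the observation period for censoring, while that same period is ignored for events. Protocol 10.3.2 uses the term differently: representatives who "refuse to participate in the study during the study period, all of their data must be excluded from the analysis dataset" do so while the study is running. On that meaning 9.1.3.2 leads to the second row. For TTF, neither Protocol 9.1.3.1 nor the SAP rows mention a study period or a last visit, so no text there points to one-sided use.

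A mixture of the first two rows across sites is also harmless under the same assumptions. Kaplan-Meier allows patients different administrative end dates, provided that within each patient one date limits both events and event-free time.

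**Late estimates.** The expected number at risk at 12 months is 70 × (18.00 − 12)/12.02 × 0.547 ≈ 19, and at 15 months 70 × (18.00 − 15)/12.02 × 0.471 ≈ 8. The 15-month estimate does not rest on those 8 alone, because it multiplies conditional survival over all earlier risk sets. SAP 8.3.1.1 already reports numbers at risk, events, censorings and confidence intervals every three months, so thin late data will be visible.

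**The case for a change.** The strongest case for a change is that derivations are programmed from SAP 6.3, and that table omits a limit that its neighbours carry. Since the SAP declares no departure from the protocol, the last-visit rule in Protocol 9.1.3.2 still stands, and a reader who equates its undefined period with the observation period gets a limit on censoring and none on events. Stating the date would cost one filter and no re-abstraction: a patient whose first event came later was event-free on 20 June 2021.

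The drafting criticism stands. So does a related gap: under SAP 6.1 a date known only to be in 2021 becomes 1 July 2021, 11 days past the cut-off, and the SAP does not say how to treat it. That affects only records lacking both month and day, and a plain date filter would not resolve it either.

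The step to bias does not follow. An analyst who takes the period as ending on 20 June 2021 has the same reason to stop events there, because Section 9.1 defines how long patients are followed. The data go into one database with site training, remote monitoring and queries (Protocol 9.6 and 9.8). SAP 6.3 ties the last progression-free confirmation to a case report form that is not among the documents and may itself carry the limit. Nor would an error necessarily shorten PFS; the opposite one-sided mistake lengthens it.

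On Section 7, it is true that only about half of patients would have more than a year of potential follow-up. The sentence does not say whether it means each patient, the median patient or the window, and an 18-month window meets it.

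**Conclusion.** No change is needed. The missing date in SAP 6.3 is a detail that analysts would supply from the study-wide observation period. Applied on both sides, it gives 6.0 to 18.0 months of potential follow-up, about 31 PFS events among 70 patients (25.5 to 36.1 for true medians of 18.0 down to 11.1 months) and no built-in bias. Literal use of the undated SAP rows is also unbiased, with about 36 to 43 events.

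If one-sided use did occur for every patient, the PFS median would be short by about 1.5 to 1.7 months, or 12-month PFS would be high by about 0.03 to 0.04, depending on which side was cut. Confined to a quarter of patients, counting late events would give a median of 13.1 to 13.3. No TTF figure was simulated.

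Limited follow-up is a real feature of the design. At a true median of 13.8 the Kaplan-Meier median is reached in about 79% of simulated studies, and its upper limit is found in only about 12-13%. That is a fair trade-off for an early look ahead of the two- and five-year studies; rewording Section 7 or the limitations in Section 9.9 would alter no result. The primary endpoint, baseline characteristics, is untouched.

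These sizes rest on even entry, exponential PFS and no loss to follow-up. A last visit up to half a month before the cut-off moves the two-sided median only to 13.6.

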## **8. RESEARCH QUESTION AND OBJECTIVES**

To describe the demographic, baseline characteristics and treatment outcomes in patients with mRCC treated with avelumab plus axitinib as a first-line therapy.

### **8.1. Primary objective**

To describe the demographic and baseline characteristics of patients with mRCC treated with avelumab plus axitinib as a first-line therapy in a real-world clinical setting.

### **8.2. Secondary objectives**

- 1) To evaluate the efficacy of avelumab plus axitinib combination therapy for patients with mRCC treated in Japan.
- 2) To describe clinical usage of corticosteroid for immune-related adverse events (irAE) during avelumab plus axitinib combination therapy period.
- 3) To describe pre-treatment and treatment for infusion-related reaction of avelumab.
- 4) To describe patterns of post progression subsequent treatments.

## **9. RESEARCH METHODS**

### **9.1. Study design**

This study is a multicenter, non-interventional, retrospective, medical chart review of patients with mRCC treated with avelumab plus axitinib as a first-line therapy in Japan between 20 December 2019 and 20 December 2020. All decisions regarding clinical management and treatment of the participating patients were made by the investigator as part of standard care in real-world clinical setting and were not contingent upon the patient's participation in the study. Data will be collected if available per study site.

- Index date: The date of first prescription for avelumab plus axitinib between 20 December 2019 (launch date) and 20 December 2020
- Observation period: Patients will be followed from index date to 20 June 2021

### **9.1.1. Primary endpoint**

- Patient characteristics at baseline
  - Age
  - Sex
  - Body mass index (BMI)
  - Eastern Cooperative Oncology Group Performance Status (ECOG PS)
  - International Metastatic RCC Database Consortium (IMDC) risk score
  - Pathological diagnosis: Fuhrman grade, histological type, Sarcomatoid component
  - Tumor-node-metastasis (TNM) classification,
  - Number of metastatic organs and site of metastases
  - Complications
  - Nephrectomy
  - Renal function: estimated glomerular filtration rate (eGFR), proteinuria
  - C-reactive protein (CRP)
  - Smoking history
  - Concomitant drugs

### **9.1.2. Secondary endpoints**

- Efficacy endpoint
  - Time to treatment failure (TTF) of avelumab plus axitinib as a first-line therapy
  - Real-world PFS
  - Objective response (OR)
- Avelumab-related endpoints
  - TTF
  - Discontinuation and interruption of avelumab
  - Reason for discontinuation and interruption
- Axitinib-related endpoints
  - TTF
  - Dose increase, dose reduction, discontinuation, and interruption of axitinib
  - Reason for dose increase, dose reduction, discontinuation, and interruption
- Corticosteroid-related endpoints
  - Cumulative dose of corticosteroid for irAE during avelumab plus axitinib treatment
  - Duration of corticosteroid treatment for irAE during avelumab plus axitinib treatment
  - Number of corticosteroid administrations for irAE during avelumab plus axitinib treatment
- Infusion-related reaction-related endpoints

- Presence of pre-medication for potential infusion-related reaction of avelumab
- Drugs of pre-medication for infusion-related reaction of avelumab
- Presence of treatment for infusion-related reaction of avelumab
- Subsequent treatment-related endpoints
  - Drugs used after avelumab plus axitinib

### **9.1.3. Definition of endpoints**

#### **9.1.3.1. Time to treatment failure (TTF)**

TTF is defined as the following:

- TTF, defined as time from start of avelumab/axitinib treatment to end of treatment for any cause earlier, including death.

#### **9.1.3.2. Real-world PFS**

Real-world PFS is defined as the following:

- Real-world PFS, defined as time from start of avelumab/axitinib treatment to date of first disease progression (as clinically assessed by local investigator based on radiology, laboratory evidence, pathology, or other assessments) or death due to any cause, whichever came first  
If there were no clinical records of death or disease progression, they were censored at the date of initiation of the next line of therapy for the patients undertaking two or more lines of therapy based on the record, or at their last visit date during the study period for the patients undertaking only one line of therapy based on the record.

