8.3 Secondary endpoint

8.3.1 Efficacy endpoint

8.3.1.1 Time-to-treatment failure (TTF) of avelumab plus axitinib as first-line therapy

Analysis set	Analysis population
Details of analysis	
The Kaplan-Meier methods is used to plot the duration of TTF and calculate survival probability (estimate, 95% confidence interval), number of patients at risk, cumulative number of events, and cumulative number of censoring every 3 months.
 
In addition, the median duration of TTF, and incidence of events (/100 person-years) and the 95% confidence interval will be calculated.

Supplement	
<Calculation method for each 95% confidence interval>
 
Survival probability: Pointwise confidence limits
 
Median duration of TTF: Greenwood exponential formula
 
Incidence of events: Mantel-Haenszel method

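### Real-world PFS: read literally, a patient who starts the next line event-free is censored there only if no progression or death is recorded later, and the SAP does not settle the point

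*Protocol*

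**What the plan says.** Protocol 9.1.3.2 takes as the event the first progression or death from any cause, with no cut-off at the start of a later line. It then sets the censoring dates. For patients with two or more lines: "If there were no clinical records of death or disease progression, they were censored at the date of initiation of the next line". For the others: "or at their last visit date during the study period for the patients undertaking only one line of therapy based on the record".

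The observation window does not end with first-line treatment. Protocol 9.1 states "Patients will be followed from index date to 20 June 2021", and Protocol 9.3.3 collects the "date of first disease progression or death due to any cause, whichever came first", again without restriction to the first line.

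The real-world PFS row of SAP 6.3 has an event column that ends "or death from any cause, whichever occurs earlier" and a censoring column that reads "Date of last confirmation of progression-free survival or start of subsequent treatment (whichever occurs earlier". SAP 8.3.1.2 applies the Kaplan-Meier analysis of SAP 8.3.1.1 to this endpoint. SAP section 9 declares no changes from the protocol.

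**The concern.** Take two patients who both start a second line in month 5 without progression. The first has progression recorded in month 11. A record of progression exists, so the censoring clause does not apply and this patient is an event at month 11. The second has no later event and is censored at month 5. Whether months 5 to 11 count as time at risk is thus decided by what happens in them.

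Kaplan-Meier requires that patients censored at a given time have the same prospects as those who stay at risk. Here the event-free time after a switch is removed and the events after a switch are kept. The result is neither PFS with all switchers censored at the switch nor PFS regardless of switching. It also counts some events that occur on another treatment. Patients who progress before they switch are handled correctly.

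The reported median, the 3-monthly probabilities and their intervals are at stake. The intervals would not reflect this error.

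**Working it through.** **1. Does the SAP remove the problem?** The event column has no limit to events before subsequent treatment. In the censoring column, the choice of the earlier date ranks two censoring dates against each other. It does not rank an event after the switch against the switch date. No other SAP text does so.

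**2. Direction.** Compare three rules: (A) the literal protocol rule; (B) every event-free switcher censored at the switch; (C) the switch ignored and everyone followed through.
- A against C: the event times are identical, and A only moves some censoring times earlier. Each Kaplan-Meier factor is 1 − d/Y, with d events among Y at risk. Since Y under A is never larger than under C, curve A can never lie above curve C.
- A against B: no such ordering exists. It has to be computed.

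**3. Inputs.**
- Entry window: "The date of first prescription for avelumab plus axitinib between 20 December 2019 (launch date) and 20 December 2020". With the cut-off of 20 June 2021, follow-up is 182 to 548 days. Divided by 30.4375 (SAP 6.2) this is 6.0 to 18.0 months, taken as uniform.
- Median 13.8 months, the trial figure in Protocol section 7, used only for scale. The times are assumed exponential, so λ = ln 2 / 13.8 = 0.0502 per month.
- Event-free switching: not in the documents. Assumed at a constant rate σ, with p = 1 − exp(−12σ) = 2, 5, 10, 20 or 30%. This is the chance of switching by 12 months in the absence of progression. In the simulation below, 10/20/30% correspond to about 7/15/22% of patients seen to switch event-free.
- Hazard after the switch: assumed equal to that before it, then varied.

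**4. Size with equal hazards.** Under B and C the hazard is λ, so 12-month PFS is exp(−12 × 0.0502) = 54.7% and the median is 13.8 months. Under A, the risk set at time t loses those who have already switched and will stay event-free to the cut-off. The hazard that Kaplan-Meier estimates is then

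h(t) = λ / [1 − (1 − exp(−σt)) × q(t)],

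where q(t) is the chance that a patient under observation and event-free at t stays so to the cut-off. At 12 months, q = (1 − exp(−6λ)) / (6λ) = (1 − 0.740) / 0.301 = 0.863. With p = 20%, h(12) = λ / (1 − 0.20 × 0.863) = 1.21λ. Integrating h(t) numerically gives:

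| Event-free switching by 12 months | 12-month PFS, rule A | Median, rule A (months) |
|---|---|---|
| 0% (equal to B and C) | 54.7% | 13.8 |
| 2% | 54.5% | 13.7 |
| 5% | 54.1% | 13.5 |
| 10% | 53.4% | 13.2 |
| 20% | 51.8% | 12.6 |
| 30% | 50.0% | 12.0 |

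A simulation of 400,000 patients per scenario gives the same figures at 10, 20 and 30%.

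**5. Unequal hazards.** With the 13.8-month median, 10 to 30% switching, and a hazard after the switch of 0.5 to 2 times that before it, rule A shifts 12-month PFS by −0.8 to −7.5 points against B and by −0.9 to −5.6 points against C. A reversal against B exists: with a 3-month first-line median and a hazard after the switch of 0.1 to 0.5 times that before it, A was 0.2 to 0.4 points above B at 6 months.

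**6. Against sampling error.** With 70 patients, S = 0.547 and no censoring before 12 months, the 95% half-width would be 1.96 × √(0.547 × 0.453 / 70) = 11.7 points. With the censoring that starts at 6 months, Greenwood's formula gives about 13 points. In 2,000 simulated cohorts of 70 (20% switching, equal hazards), A never exceeded C at 3, 6, 9 or 12 months. It averaged 2.9 points below either rule at 12 months, and was below B there in 90% of cohorts.

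**The case against.** A reader might infer that the planned PFS analysis will be biased downward. The documents do not support that as settled, for four reasons.

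- **The SAP may intend the sound rule.** Protocol 9.7 leaves detailed methods to the SAP and lets it modify the protocol. SAP 6.3 drops the protocol's condition about missing event records and lists the start of subsequent treatment as a censoring date, so a programmer could reasonably censor every switcher there. This stands as a possible reading. It does not dispose of the point, because the SAP never says so and declares no changes from the protocol.
- **The size is unknown.** Neither document gives the share who switch without progression. At 2 to 5% with equal hazards the median moves by only 0.1 to 0.3 months. This stands.
- **Capture after the switch is uncertain.** Protocol 9.1 collects data where the site has them, and for the second line Protocol 9.3.9 lists only medication. Protocol 9.3.3 does not stop at the switch, and SAP 8.3.6 tabulates time to death or last confirmed survival, so later deaths at least are sought. How fully later progression is captured cannot be told.
- **The stakes are limited.** The primary endpoint is baseline characteristics, no hypothesis is tested, and Protocol section 12 says the results are not part of any regulatory submission. This stands and lowers the severity. A systematic error nonetheless remains, whatever the width of the interval.

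**Conclusion.** The point holds as a defect in the written rule. Protocol 9.1.3.2, taken literally, makes censoring depend on later outcome, and SAP 6.3 leaves the handling of an event after the switch open.

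A downward shift is certain only against following every switcher through. Against censoring all switchers at the switch it is usual but not guaranteed. For 10 to 30% event-free switching with equal hazards, the loss is about 0.6 to 1.8 months in the median and 1 to 5 points at 12 months; at 2 to 5% it is negligible. These sizes rest on exponential times, a borrowed 13.8-month median, uniform entry and an assumed switching share.

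Severity is moderate. The endpoint is secondary and descriptive, and the bias in the equal-hazard cases is well below the sampling error of about 13 points. It is still worth correcting, because the correction is almost free and more patients would not remove the error.

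**What to change.** Before data lock, put one rule in Protocol 9.1.3.2 and in the PFS row of SAP 6.3 for every patient who starts subsequent therapy without earlier recorded progression. For example: progression or death counts as an event only if it occurs on or before the start of subsequent therapy, and every other patient who starts such therapy is censored at that start, whatever is recorded later. This keeps the switch date that both documents already name for censoring.

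Add the other consistent rule as a supportive curve: follow all switchers to progression, death or last assessment up to 20 June 2021. Report the number of event-free switchers, and how many of them have a later recorded event.

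Either rule could be the main analysis, provided that it applies to all switchers alike. Censoring at the switch leaves fewer events, sets aside deaths after the switch, and may itself be informative; the supportive curve shows how much this matters. The cost is a sentence in each document and one more curve. The main rule needs only the next-line start date that the present rule already requires. The supportive curve is limited by how fully sites recorded progression after the switch.
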